**Figure 5 Dosing Schema of LT3001 and Dabigatran Co-administration**

**5.2. Participant and Study Completion**

Approximately 16 subjects (8 Chinese and 8 non-Asian) will be enrolled in Part A and 48 subjects in Part B. A subject will have completed the study when the final PK and safety assessments are done at the end-of-study (EOS) or follow-up visit.

**5.3. End of Study Definition**

The end of the study is defined as the date of the last visit of the last participant in the study.

**5.4. Scientific Rationale for Study Design**

Studies comparing the PK and safety of a drug product in Chinese and non-Asian subjects allow for extrapolation of clinical data across regions. Use of healthy participants rather than patients minimizes confounding factors due to disease. Randomization and blinding minimizes bias in the assessment of safety and interpretation of results. The susceptibility of LT3001 to drug interaction will be assessed by measuring LT3001 when administered alone and in combination with aspirin, apixaban, clopidogrel, and dabigatran. Similarly, the effect of LT3001 on aspirin, apixaban, clopidogrel, and dabigatran will be assessed by measuring those analytes alone and in combination with LT3001.

**5.5. Justification for Dose**

[REDACTED]. There were no clinically significant changes in safety parameters and AUC was within the predetermined bounds.

## 6. Study Population

Prospective approval of protocol deviations to recruitment and enrollment criteria, also known as protocol waivers or exemptions, is not permitted.

### 6.1. Inclusion Criteria

Participants are eligible to be included in the study only if all of the following criteria apply:

1. Signed the informed consent form (ICF) as described in [Appendix 3](#) which includes compliance with the requirements and restrictions listed in the ICF (ICF) and in this protocol
2. Subject is a male or female between 18 and 65 years of age on the day of screening.
3. Subject's body weight is  $\geq 50$  kg and body mass index is within the range of 18 to 32 kg/m^2 (inclusive).
4. Subject is a healthy volunteer confirmed by a comprehensive clinical assessment, including detailed medical history, a complete physical examination, fasting blood glucose, vital sign measurements, ECG results, and laboratory investigations (hematology, clinical chemistry, and urinalysis). The results should be clinically acceptable for healthy subjects per the principle Investigator's assessment.
5. Subject's PT, aPTT, and TT are within the normal laboratory range.
6. Female subject must be of non-childbearing potential or, if of child-bearing potential, must be using medically acceptable contraceptive measures ([Appendix 5](#)) throughout the duration of the study and for at least 30 days after receiving the last dose of study treatment. A woman of nonchildbearing potential is defined as a woman who is over 55 years old and postmenopausal at least 12 months prior to screening or a woman who is surgically sterile.
7. Male subjects and their partners of childbearing potential must commit to the use of medically acceptable contraception ([Appendix 5](#)) for the study duration. Men must refrain from donating sperm during this same period. The female partners should be asked to use a contraception method that is medically acceptable, and these contraceptive measures should be used throughout the duration of the study and for at least 30 days after their last dose of study treatment.
8. Subject is a nonsmoker (abstinence for at least 6 months prior to screening).
9. A Chinese subject is defined as a first-generation Chinese (both parents of Chinese descent) who maintains a typical Chinese lifestyle, including diet. In addition to mainland China, subjects or their parents may also be from Taiwan, Hong Kong, or Mongolia.

Note: Retesting of abnormal lab values that may lead to exclusion will be allowed once. Retesting will take place during an unscheduled visit in the screening phase.

## 6.2. Exclusion Criteria

Participants are excluded from the study if any of the following criteria apply:

1. Subject has a positive result from an alcohol or drug test for amphetamines, barbiturates, cocaine, opiates, cannabinoids, or benzodiazepines during screening.
2. Subject has a positive result from a hepatitis B virus (HBV) test (hepatitis B surface antigen; HBsAg) or hepatitis C virus (HCV) test (anti-HCV antibody) within 3 months of screening.
3. Subject has a history of HIV infection.
4. Subject has a current or recent history (within 6 months prior to screening) of regular alcohol consumption (ie, at least 2 ounces of alcohol or 2 drinks per day).
5. Subject has received any investigational product within 30 days or 5 half-lives (whichever is longer) prior to the first dosing day or is planning to participate in a clinical trial during the study period.
6. Subject has used prescription or nonprescription drugs, including vitamins, herbal and dietary supplements within 7 days prior to the first dose of study drug, unless the medication will not interfere with the study procedures or compromise subject safety in the opinion of the Investigator.
7. Subject has a history of sensitivity to any of the study drugs or components thereof, or a history of drug or other allergy that, in the opinion of the Investigator, contraindicates participation.
8. Subject has donated blood or blood products within 56 days prior to screening.
9. Female subject of childbearing potential has a positive result for serum pregnancy test on Day -1.
10. Male subject is planning a pregnancy with a female partner from screening until 30 days after completing study drug treatment.
11. Subject is unwilling or unable to follow the procedures outlined in the protocol in the opinion of the Investigator.
12. Subject has a presence or history of coagulation abnormality.
13. Subject has abnormal laboratory values or clinical findings on screening that are judged clinically significant by the Investigator.
14. Subject has a history of clinically significant renal or liver dysfunction.
15. Subject has a presence or history of psychiatric illness or mental impairment.
16. Subject has a significant risk for suicidal behavior in the opinion of the Investigator.
17. Subject has a history of long QT syndrome (personal or family) or cardiac conduction disorder, or clinically significant cardiac disease.
18. Urinary cotinine levels at screening are indicative of smoking or subject has history of regular use of tobacco- or nicotine-containing products prior to screening.
19. Subject is an employee (permanent, temporary contract worker, or designee responsible for the conduct of the study) of the Investigator or study site, or immediate family\* of such employees or the Investigator.
20. Subject is an employee or immediate family\* of an employee of Lumosa Therapeutics Co., Ltd. or contract research organization conducting the trial.

(\*Immediate family is defined as a spouse, parent, child, or sibling, whether biological or legally adopted.)

21. Subject has an active infection of coronavirus disease 2019 at screening.

22. Subjects who are enrolled in Part B and allergic to acetylsalicylic acid, other salicylates, clopidogrel, thienopyridines (eg, ticlopidine, prasugrel), apixaban or dabigatran.
23. Subjects who are enrolled in Part B and taking medications that affect the PK characteristics of aspirin, clopidogrel, apixaban or dabigatran.
24. Subjects need to receive a surgery or clinical procedures associated with high bleeding risk.
25. Part B Cohort 2 only: subjects who are poor metabolizers of clopidogrel (CYP2C19\*2/\*2, \*2/\*3, or \*3/\*3 genotype)
26. Subject has a history of minor bleeding episodes, eg, epistaxis, rectal bleeding, gingival bleeding.
27. Subject has a history of peptic ulcer or gastrointestinal bleeding.

### **6.3. Lifestyle Restrictions**

#### **6.3.1. Meals and Dietary Restrictions**

1. Refrain from consumption of red wine, Seville oranges, grapefruit or grapefruit juice, pomelos, exotic citrus fruits, grapefruit hybrids, or fruit juices from 3 days before the start of study treatment until after the final dose.

#### **6.3.2. Caffeine, Alcohol, and Tobacco**

1. Subjects will abstain from ingesting caffeine- or xanthine-containing products (eg, coffee, tea, cola drinks, and chocolate) for 24 hours before collection of any PK sample until after collection of the final PK sample.
2. Subjects will abstain from alcohol for 24 hours before the first dose until after collection of the final PK sample.
3. Use of tobacco products will not be allowed during the study.

#### **6.3.3. Activity**

1. Subjects will abstain from strenuous exercise for 24 hours before each blood collection for clinical laboratory tests. Subjects may participate in light recreational activities during studies (eg, watching television, reading).

### **6.4. Screen Failures**

Screen failures are defined as participants who consent to participate in the clinical study but are not subsequently randomly assigned to study treatment or entered in the study. A minimal set of screen failure information is required to ensure transparent reporting of screen failure participants to meet the Consolidated Standards of Reporting Trials (CONSORT) publishing requirements and to respond to queries from regulatory authorities. Minimal information includes demography, screen failure details, eligibility criteria, and any SAE.

Individuals who do not meet the criteria for participation in this study (screen failure) may not be rescreened.

## 7. Treatments

Study treatment is defined as any investigational treatment(s), marketed product(s), placebo, or medical device(s) intended to be administered to a study participant according to the study protocol.

### 7.1. Treatments Administered

**Table 6 Identity of Study Treatments**

Study Treatment Name	LT3001 drug product	Placebo	Aspirin	Clopidogrel	Apixaban	Dabigatran
Dosage formulation	solution	solution	tablet	tablet	tablet	capsule
Dosage level(s)						
Route of Administration	IV infusion	IV infusion	Oral	Oral	Oral	Oral
Dosing instructions Part A	15 minute infusion TID q3h for 3 days	NA	NA	NA	NA	NA
Dosing instructions Part B						
Packaging and Labeling	Study Treatment will be provided in a vial. Each vial will be labeled as required per country requirement.		Commercial packaging			
Manufacturer						

### 7.2. LT3001 Drug Product and Placebo

LT3001 drug product will be provided as a preservative-free, sterile, lyophilized powder for injection in glass vials with butyl rubber stoppers and flip-off aluminum crimp seals. Each vial will contain LT3001 drug substance, equivalent to 20 mg free base, as a white to off-white lyophilized cake or powder. Placebo is formulated identically in the components, composition, and appearance to LT3001 drug product but does not contain the active compound. The LT3001 drug product should be stored at 2°C to 8°C (35.6°F to 46.4°F).

The dose level of LT3001 drug product will be calculated by the Investigator or a qualified designee based on the subject's body weight and confirmed by the unblinded pharmacist before study treatment preparation.

LT3001 drug product and placebo should be reconstituted prior to use with normal saline (0.9% Sodium Chloride) to a final concentration of 4 mg/mL. LT3001 drug product will be further diluted to a suitable concentration with normal saline and administered via a 15-minute IV infusion. Instructions for reconstitution and dilution will be provided separately to the sites.

The reconstituted LT3001 drug product and placebo solution could be stored at room temperature for 8 hours or at 2°C to 8°C (35.6°F to 46.4°F) for 24 hours.

Drug supplies of LT3001 drug product and placebo will be provided by the Sponsor.

### **7.3. Dose Modification**

No changes to doses or dosing schedule are allowed.

### **7.4. Method of Treatment Assignment**

In Part A, the first four sentinel subjects will be randomly assigned to LT3001 drug product or placebo in a 1:1 ratio. The remaining subjects will be randomized in a 3:1 ratio.

In Part B, subjects will be sequentially assigned to one of four treatment cohorts.

### **7.5. Randomization Procedures**

In Part A, in order to preserve the blinding of the subject or the personnel involved in subject evaluations or data collection, an unblinded pharmacist who is not directly involved in the study conduct, data management, or data analysis will be designated. The Investigator or designee should provide the necessary information to the unblinded pharmacist who will obtain the assignment of the subject's treatment according to the randomization code list. Neither the subject nor the Investigator will know the treatment to which the subject has been assigned.

### **7.6. Maintenance of Randomization Codes**

In Part A, randomization codes will be provided to the unblinded pharmacist who prepares study treatments and the unblinded biostatistician(s) perform the PK analysis at the beginning of Part A. The pharmacist will use the randomization code list for treatment assignment and preparing subject doses throughout the study.

### **7.7. Blinding**

Part A is double-blind. The unblinded pharmacist at the study site will prepare the study drug. In order to protect the blinding of the subjects and Investigators, the IV bag will be masked properly. Because of the double-blind design of Part A, the Investigator or designee should treat and evaluate all subjects as though they received LT3001 drug product. Only the pharmacist responsible for treatment

assignment and the biostatisticians generating the randomization code or performing the unblinded PK analyses will be unblinded and will have access to treatment assignments; all other parties involved in the study will be fully blinded until Part A is completed.

For the safety review meeting of Part A, a blinded PK analysis will be conducted after all healthy subjects complete study procedures of Part A and blood PK data will be reviewed in a blind manner in the meeting.

Part B is open-label.

### **7.8. Breaking the Blind**

A subject's treatment assignment will not be broken until the end of Part A unless, in the Investigator's opinion, knowledge of treatment assignment would alter management of SAEs or non-serious AE of Grade 3 or higher severity. In the event that the blind needs to be broken because of a medical emergency, the Investigator may be unblinded to obtain the subject's treatment assignment. Prior to unblinding a subject's treatment assignment, the Investigator should make every effort to contact the medical monitor to discuss the medical emergency and the reason for revealing the actual treatment received by that subject. If a subject's treatment is unblinded, Lumosa must be notified immediately. The Investigator or designee must clearly document any unblinding event and the documentation must include the subject number, the reasons for treatment unblinding, and the date on which the code was broken.

### **7.9. Preparation/Handling/Storage/Accountability**

The Investigator or designee must confirm appropriate temperature conditions have been maintained during transit for all study treatment received and any discrepancies are reported and resolved before use of the study treatment.

Only participants enrolled in the study may receive study treatment and only authorized site staff may supply or administer study treatment. All study treatments must be stored in a secure, environmentally controlled, and monitored (manual or automated) area in accordance with the labeled storage conditions with access limited to the Investigator and authorized site staff.

The Investigator, institution, or the head of the medical institution (where applicable) is responsible for study treatment accountability, reconciliation, and record maintenance (ie, receipt, reconciliation, and final disposition records).

The Investigator will maintain accurate records of drug disposition required by applicable law, including date and quality administered, and subject to whom study drug was administered. Reasons for departure from the expected dispensing regimen must also be recorded.

A study drug accountability log will be used to document study drug disposition. All items on the log are to be completed in full. The study clinical research associate will ensure that the area where the study drug accountability records are to be maintained is adequate.

Each time the pharmacist designated by the Investigator dispenses study drug for a subject, he or she is to record the subject number and initials, randomization number, date dispensed, number of vials of study drug dispensed, and his or her initials. The study clinical research associate will count all used and unused containers of study drug and review study drug accountability records during routine monitoring visits. The clinical research associate will also need to verify dose calculation to check whether the actual doses administered were the same as those intended.

At the completion of the study, to satisfy regulatory requirements regarding drug accountability, the amount of study drug will be reconciled and retained on site, the unused study drug will be arranged for return to the sponsor, or destruction according to site's standard protocols.

## **7.10. Treatment Compliance**

LT3001 drug product will be administered via an IV infusion by the Investigator or qualified personnel. Aspirin, clopidogrel, dabigatran, and apixaban will be orally administered under the direct supervision of the Investigator or designee. A hand and mouth check will be done to ensure that the medication was swallowed.

## **7.11. Concomitant Therapy**

Any medication or vaccine (including over-the-counter or prescription medicines, vitamins, and/or herbal supplements) that the subject is receiving at the time of enrollment or receives during the study must be recorded along with:

- Reason for use
- Dates of administration including start and end dates
- Dosage information including dose and frequency

The Medical Monitor should be contacted if there are any questions regarding concomitant or prior therapy.

Except as note below, subjects must abstain from taking prescription or nonprescription drugs (including vitamins and dietary or herbal supplements) within 7 days (or 14 days if the drug is a potential enzyme inducer) or 5 half-lives (whichever is longer) before the start of study treatment until completion of the follow-up visit, unless, in the opinion of the Investigator and sponsor, the medication will not interfere with the study. In particular, any medication which affects blood pressure or coagulation functions is prohibited.

Acetaminophen, at doses of  $\leq$  2 grams/day, is permitted for use at any time during the study. Oral contraceptives and hormone replacement therapy are also allowed. Other concomitant medication may be considered on a case-by-case basis by the Investigator in consultation with the Medical Monitor.

### **7.11.1. Rescue Medicine**

There is no rescue medication for this study.

## **7.12. Treatment after the End of the Study**

Subjects will not receive study medication after the end of the study.

## **8. Discontinuation/Withdrawal Criteria**

### **8.1. Discontinuation of Study Treatment**

If a clinically significant AE is identified after enrollment, the Investigator or Medical Monitor will determine if the subject can continue in the study and if any change in subject management is needed.

In Part A, dosing of an individual subject will be discontinued in the event of the following:

- Clinically significant changes in coagulation parameters, which indicate that hemorrhage might occur.
- Subject experiences an AE of Grade 3 or higher severity
- Investigator or designee determines that discontinuation of dosing is in the best interest of the subject

In Part B, dosing of an individual subject will be discontinued in the event of the following:

- Subject experiences an AE of Grade 3 or higher severity
- Investigator or designee determines that discontinuation of dosing is in the best interest of the subject

Part A and each cohort of Part B will be terminated when two subjects within the same cohort experience any study drug related SAE or non-serious AE of Grade 3 or higher severity (at least possibly related).

See the Schedule of Activities (SoA, [Section 2](#)) for data to be collected at the time of treatment discontinuation and follow-up and for any further evaluations that need to be completed.

#### **8.1.1. Temporary Discontinuation**

If a non-serious AE which resulted in discontinuation resolves without sequelae, the Investigator may allow the subject to re-join the study within the same cohort.

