#### Safety Review Schema

## Part B

Part B is open-label without placebo control. Approximately 48 subjects will be sequentially enrolled into four cohorts with 12 subjects in each cohort.

The first **3** subjects of each cohort will be “sentinel subjects”. After each sentinel subject completes the first day of combination treatments, the Investigator will review all available safety data from the sentinel subjects. If considered safe to do so, each sentinel subject will receive the remaining combination treatments.

The remaining combination treatments in a sentinel subject may not proceed in the event of any of the following:

- A subject experiences any severe hemorrhage which is assessed as related to the combination treatment
- A subject treated with LT3001 drug product experiences any SAE related to study drug (at least possibly related)
- Safety concerns per the Investigator’s clinical judgment

The dosing schema is summarized below.

Each Cohort of Part B	Sentinel Subjects	Remaining Subjects
Number of Subjects	3	9

In **Cohort 1**, each subject will receive a single 15-minute infusion of LT3001 [REDACTED] on Day 1. Each subject will receive multiple-dose aspirin as follows: a loading dose of 325 mg aspirin on the morning of Day 2 followed by a daily maintenance dose of 81 mg aspirin on Days 3 through 8 (Figure 2). The regimen is intended to achieve its maximal inhibitory effects on platelet function. Aspirin will be administered after breakfast. On the morning of Day 6, the dose of aspirin will be followed by the first dose of LT3001 0.025 mg/kg administered as a 15-minute IV infusion. Subjects will receive 9 doses of LT3001 on Days 6 through 8 (TID q3h). Each subject will be admitted into the study site on Day -1, stay until Day 8, and will have a follow-up visit on Day 15.

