#### **8.1.2. Rechallenge**

Subjects who temporarily discontinued study treatment due to a non-serious AE will be closely monitored during rechallenge. A recurrence of the original AE, or a worsening of the AE, will result in permanent discontinuation of that subject from the study.

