### **8.2. Withdrawal from the Study**

The study inclusion and exclusion criteria for enrollment must be followed explicitly. If a subject who does not meet enrollment criteria is inadvertently enrolled, that subject shall be withdrawn from the study.

A subject may withdraw from the study at any time at his/her own request, or may be withdrawn at any time at the discretion of the Investigator for safety, behavioral, compliance, or administrative reasons.

Additionally, this study may be terminated at the discretion of the Sponsor. The Sponsor may stop the study at any time for safety, regulatory, legal, or other reasons aligned with Good Clinical Practice (GCP).

If the subject withdraws consent for disclosure of future information, the sponsor may retain and continue to use any data collected before such a withdrawal of consent.

If a subject withdraws from the study, he/she may request destruction of any samples taken and not tested, and the Investigator must document this in the site study records.

See SoA for data to be collected at the time of study discontinuation and follow-up and for any further evaluations that need to be completed. All the enrolled subjects withdrawn from the study are encouraged to complete all end-of-study (EOS) or early termination (ET) assessments.

When a subject withdraws from the study, the reason(s) for withdrawal shall be recorded by the Investigator in the subject's source documents and on the relevant page of the electronic case report form (eCRF).

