## 9. Study Assessments and Procedures

Study procedures and their timing are summarized in the SoA ([Section 2](#)). Total volume of blood per subject in each cohort summarized in the Table 7.

Protocol waivers or exemptions are not allowed. Immediate safety concerns should be discussed with the sponsor immediately upon occurrence or awareness to determine if the subject should continue or discontinue study treatment. Adherence to the study design requirements, including those specified in the SoA, is essential and required for study conduct.

All screening evaluations must be completed and reviewed to confirm that potential participants meet all eligibility criteria. The Investigator will maintain a screening log to record details of all subjects screened and to confirm eligibility or record reasons for screening failure, as applicable.

Procedures conducted as part of the subject's routine clinical management (eg, blood count) and obtained before signing of the ICF may be utilized for screening or baseline purposes provided the procedures met the protocol-specified criteria and were performed within the time frame defined in the SoA.

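### Protocol 8.1.1 lets the Investigator alone re-dose a healthy volunteer after a related, non-serious Grade 3+ AE, a class that 8.1 treats alongside SAEs

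*Protocol*

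**What the plan says.** Protocol 8.1 lists the reasons for stopping an individual's dosing. In both Part A and Part B, an AE of Grade 3 or higher is one of them, and the stop is mandatory. The same section ends Part A, or a Part B cohort, when "two subjects within the same cohort experience any study drug related SAE or non-serious AE of Grade 3 or higher severity", with relatedness set at possible or stronger. For a clinically significant AE, it also says that "the Investigator or Medical Monitor will determine if the subject can continue in the study".

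The next subsection, 8.1.1, opens a way back: "If a non-serious AE which resulted in discontinuation resolves without sequelae, the Investigator may allow the subject to re-join the study within the same cohort". Section 8.1.2 adds close monitoring during rechallenge and this consequence: "A recurrence of the original AE, or a worsening of the AE, will result in permanent discontinuation of that subject from the study".

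Two other places bear on the point. Section 7.8 allows the blind to be broken to manage SAEs or non-serious AEs of Grade 3 or higher. Appendix 4 (Assessment of severity) states that seriousness depends on the outcome criteria and not on the severity rating.

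**The concern.** The protocol treats a related, non-serious Grade 3+ AE as grave in two ways: it must stop the subject's dosing, and it brings the cohort halfway to termination. Section 8.1.1 then allows the same subject to be dosed again on one person's decision, once the event has resolved. Grade, which triggered the stop, plays no part in the decision to restart.

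The people exposed are healthy volunteers, who gain nothing from a second exposure. LT3001 is described in 3.2.1 as designed to have thrombolytic activity, and in Part B the re-exposure can come on top of an antiplatelet or anticoagulant. This is a permission written into the protocol rather than a silence that judgment would have to fill, so a site that used it would be complying.

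**Working it through.** **Rule logic.** The documents give no operating characteristic for these rules, so there is no figure to reproduce. The check is to take each kind of AE through 8.1 and 8.1.1.

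| AE | Individual stop (8.1) | Counts towards cohort termination (8.1) | Re-joining (8.1.1) |
|---|---|---|---|
| Serious, related | Mandatory if Grade 3+, otherwise by judgment | Yes | No route: 8.1.1 covers non-serious AEs only |
| Non-serious, Grade 3+, at least possibly related | Mandatory | Yes | Allowed once resolved without sequelae |
| Non-serious, Grade 3+, not related | Mandatory | No | Allowed once resolved without sequelae |
| Non-serious, Grade 1-2 | By judgment (Part A also lists coagulation changes) | No | Allowed once resolved without sequelae |

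Rows 1 and 2 are treated alike for cohort termination but differently for re-dosing. Row 2 is the inconsistency.

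**Is row 2 empty?** No. Sections 8.1 and 7.8 both name non-serious Grade 3+ AEs as a class, and Appendix 4 separates serious from severe. But the row is thin. Appendix 4 describes Grade 3 partly by an indication for hospitalization or its prolongation. Hospitalization or prolongation makes an event serious, doubt on that point is resolved towards serious, and important medical events should usually be classed as serious. Grade 4 and 5 events would normally be serious as well. What remains is mainly related, non-serious Grade 3.

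**Who decides?** Section 8.1.1 names the Investigator. The continuation decision in 8.1 is worded as Investigator or Medical Monitor, so it does not oblige the two to agree.

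**How much time is there?** From the schedules of activities, the first to the last combination infusion spans 175 − 121 = 54 h in Cohort 1, 199 − 145 = 54 h in Cohort 2 and 151 − 97 = 54 h in Cohorts 3 and 4. In Part A, Dose 1 to Dose 9 spans 55 − 1 = 54 h. An AE that starts in that window has to resolve within it for re-dosing to be possible. In Part B, AEs after the Day 1 infusion or on the co-medication alone have longer.

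**Price of losing one subject's pair.** Inputs: 12 subjects per Part B cohort (Protocol 5.1) and 90% CIs from a model with Day fixed and subject random (SAP 8.3), treated here as a paired comparison. The log-scale half-width is proportional to t(0.95, n − 1)/√n.

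- n = 12: 1.7959/√12 = 0.5184
- n = 11: 1.8125/√11 = 0.5465
- Ratio: 0.5465/0.5184 = 1.054, so about 5% wider whatever the variability

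The documents give no within-subject CV. With s = √ln(1 + CV²), the CI limits lie a factor exp(t·s·√(2/n)) either side of the ratio:

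| Assumed CV | n = 12 | n = 11 |
|---|---|---|
| 10% | 1.076 | 1.080 |
| 20% | 1.156 | 1.165 |
| 40% | 1.326 | 1.347 |

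**The case against.** The best defence is that rechallenge is left to clinical judgment in an inpatient unit with supervised dosing, and that several protections surround it. Re-joining is optional. A recurrence ends the subject's participation. Section 9 says "Immediate safety concerns should be discussed with the sponsor immediately upon occurrence or awareness", and 8.2 says "The Sponsor may stop the study at any time for safety, regulatory, legal, or other reasons". It can also be argued that the Grade 3+ stop in 8.1 was meant as permanent, with 8.1.1 reaching only discretionary stops. All of this bears on likelihood, and it keeps the point modest. It does not remove the inconsistency: none of these provisions limits rechallenge by grade or requires a second person's agreement, and the text does not mark the Grade 3+ stop as permanent.

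Two stronger readings are tempting, and neither is supported.

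- A reader might infer that the two-subject rule is defective, because a related Grade 3+ AE that recurs in the same person leaves the count at one. But the rule counts subjects, and not counting one person twice is normal for such a rule. The first event already stands as one of two, any second affected subject ends the cohort, and 8.1.2 removes the rechallenged subject.
- A reader might infer that the nine non-sentinel subjects in a Part B cohort lack a stop that the three sentinels have. For sentinels, 5.1 says "The remaining combination treatments in a sentinel subject may not proceed in the event of any of the following", and the list includes "A subject experiences any severe hemorrhage which is assessed as related to the combination treatment". But the Grade 3+ stop in 8.1 binds all 12, 8.1.1 applies to sentinels and non-sentinels alike, and a severe hemorrhage would often be serious and so outside 8.1.1.

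**Conclusion.** The point stands as an internal inconsistency. Section 8.1.1 selects on seriousness and recovery alone, whereas 8.1 and 7.8 put non-serious Grade 3+ AEs next to SAEs. The consequence is a written permission for the Investigator alone to re-dose a healthy volunteer after a related, non-serious Grade 3 AE.

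Its reach is small. The class is narrow and the dosing window short. The single-dose study is reported in 3.3 as showing no clinically significant safety changes at this dose. The documents give no rate of Grade 3+ AEs and nothing on how often such events would resolve in time, be rechallenged or recur, so any frequency would be a product of guesses and none is offered. The case rests on the inconsistency and the low cost of removing it. No endpoint, estimate or planned analysis is wrong because of it.

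**What to change.** In 8.1.1, state that a subject whose discontinuation was due to an AE of Grade 3 or higher, at least possibly related to study treatment, may not re-join, and require medical monitor agreement for any other rechallenge. Section 7 already defines study treatment to include the marketed co-medications and placebo, so the limit would cover them. This closes the gap by itself; the two-subject rule and 8.1.2 can stay as written.

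The change adds no visits or samples. Under 8.4 a subject withdrawn for an LT3001-related safety reason is not replaced, so a cohort may occasionally lose a later profile. If the AE follows the first sampled combination infusion, the pair for the effect on LT3001 (Day 1 and Day 6 in Cohort 1) is already complete. The co-medication pair (Day 5 and Day 8) and the first-to-last-dose accumulation pair are the ones at risk, at the 5% widening shown above. Sample sizes were not set on statistical grounds (Protocol 10.1, SAP 4.1), so no planned power is given up.
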